5.2 Randomized Intervention Study

Primary outcome

Proportion of patients prescribed an antibiotic in each arm by day 28.

The following information will be collected to assess the proportion of patients prescribed an antibiotic in each arm by day 28:

- Day of the antibiotic prescription
- Antibiotic substance prescribed
- Dosage of antibiotic prescribed
- Duration of the antibiotic treatment prescribed

Secondary Outcomes

Clinical outcomes

- a. Duration of the episode: number of days during which the patient was symptomatic (defined by the daily symptom diary and telephone follow-up) within 28 days of follow-up.
- b. Duration of restricted daily activities: number of days during which the patient's daily activities (work or recreation) were restricted due to a respiratory tract infection.
- c. Clinical failure by day 7:
 - i. Admission to hospital within 7 days of follow-up
 - ii. Death within 7 days of follow-up
 - iii. No amelioration or worsening of relevant symptoms (fever and/or dyspnoea) at day 7
- d. Number of medical visits for the episode of LRTI within 28 days of enrolment.
- e. Serious adverse outcome: measured by day 28, based on the advent of at least one of the following events:
 - i. Death
 - ii. Secondary admission to hospital for any reason
 - iii. Complications (persistence of pneumonia, lung abscess, lung effusion, empyema or sepsis)
- f. Number of days with side effects related to antibiotics within 28 days of follow-up

The following information will be collected during telephone follow-up and recorded in the eCRF. It will also be obtained from the patient's diary.

Consultation process

- a. Median duration of time spent for the medical consultation, blood sampling, PCT measurement, lung US and total time spent in the practice.
- b. Quality of the ultrasound images. Agreement between GPs and experts on ultrasound images interpretation.
- c. Evaluation of the satisfaction of providers and of patients.

Economic aspects

- a. Cost / effectiveness ratio expressed as amount of money required per 1% absolute decrease of the proportion of antibiotic prescription.

Exploratory Outcomes

- a. Prevalence of different respiratory pathogens assessed by multiplex rt-PCR on nasopharyngeal swab and sputum
- b. Sensitivity and specificity of combinations of host biomarkers and gene expression signatures in identifying patients with serious adverse outcome, clinical failure or with pneumonia

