An individual patient may also choose to refuse the phone interview, without discontinuing the study itself. In this case, the investigators can access the medical file until the end of the 28 days observation period.

There are no foreseeable reasons for investigators to withdraw a patient from the study. Patients who are not reachable during follow-up will not have outcome data. They will be excluded from the analysis of the safety of the intervention but they will still be included in the assessment of impact on antibiotic treatment and of the feasibility of the intervention.

Physicians may choose to discontinue participating in the study. If so, they are responsible of informing the study team. If discontinuation occurs before the training and randomisation session, they will be replaced by another willing physician. If discontinuation occurs after patient recruitment, training and randomisation, patient outcomes will be collected by the study staff until the end of planned follow-up. Access to the medical files will be discussed on a case by case basis with the physician.

There is no foreseeable reason for the investigators to withdraw a physician from the study once he participated in patient recruitment, training and randomisation.

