9.2 Assessments of outcomes

Assessment of primary outcome

Pilot Study

Assessment of the outcomes of the pilot study has been described in section 8.5.1.

Randomized intervention study

Assessment of the outcomes of the randomized intervention study has been described in section 8.5.2.

Assessment of secondary outcomes

Pilot Study

Assessment of the outcomes of the pilot study has been described in section 8.5.1.

Randomized intervention study

Assessment of the outcomes of the randomized intervention study has been described in section 8.5.2.

Assessment of other outcomes of interest

Assessment of the exploratory outcomes has been described in section 8.5.2.3

Assessment of safety outcomes

Adverse events

The GP will be asked to record any serious adverse events (hospitalization, death) within 7 days into the eCRF. Any new recording of severe adverse events (SAE) will be automatically notified to the PI. Adverse events recorded by telephone follow-up will also be recorded

Laboratory parameters

In the intervention arms, prescription of laboratory tests (other than PCT POCT) will be at the discretion of the participating physicians. They will follow their usual routine, either for tests performed in house or sent to an external laboratory. No additional quality control or standard procedures are planned for this aspect.

Vital signs

Vital signs will be assessed with the usual equipment available to the GP at his practice. Measurement is expected to reflect routine practice, and as such no standardized measurement protocol or calibration procedures are planned.

Assessments in participants who prematurely stop the study

Patients will be considered lost to follow-up if telephone interviews were not feasible. A patient may change GP over the course of the study, without this affecting his participation in the study. Phone interviews will continue.

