11.4 Planned Analyses

Datasets to be analysed, analysis populations

The analysis will be performed in intention to treat (pragmatic trial). The analysis population will comprise all patients included by the randomised GPs. The primary analysis will include all patients enrolled in the study, irrespective of follow-up. Patients who are lost to follow-up will be considered as having had a clinical failure, an adverse outcome and duration of disease equal to the maximum duration measured in the other patients. Patients in whom GPs did not follow the respective algorithm recommendation and/or who did not have complete telephone follow-up will be excluded from the per-protocol analysis.

Primary Analysis

Odds ratio of antibiotic prescription between 2 groups as well as the difference in proportion of patients prescribed an antibiotic by day 28 using logistic regression corrected for variation at the GP level (generalized linear mixed effect)

Secondary Analyses

The following statistical analyses are planned:

- Difference between the mean number of days with restricted activities by day 14 using linear mixed effect regression
- Difference between the mean number of medical consultations by day 28 using linear mixed effect regression
- Odds ratio of adverse outcome between 2 groups as well as the difference in proportion of patients with adverse outcome and clinical failure using logistic regression corrected for variation at the GP level (generalized linear mixed effect)
- Difference between the mean daily symptom scores measured in the different arms. The effects of the interventions on recovery will be studied by comparing the slopes of symptom scores over time between arms
- Difference in the mean duration of total time spent in the practice using linear mixed effect regression
- Difference in levels of satisfaction of providers and of patients between arms
- Difference in the mean cost per arm using linear mixed effect regression
- Diagnostic performance of:
 - individual host biomarker(s) based on crude positive and negative likelihood ratios, and on the area under the curve of receiver operator characteristic (ROC) curves, to predict the development of a life-threatening disease, clinical failure, or the presence of pneumonia (using a clinical diagnosis).

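### The per-protocol set excludes anyone without complete telephone follow-up, even when an event is known, so any per-protocol analysis of adverse outcomes would lose deaths before the day-28 call

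*Combined protocol and SAP*

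**What the plan says.** Section 11.4 (analysis populations) makes intention to treat the main analysis and gives two grounds for leaving the per-protocol set. One is that the GP did not follow the algorithm. The other applies to patients "who did not have complete telephone follow-up will be excluded from the per-protocol analysis". This is the only mention of a per-protocol analysis, and no outcome is assigned to it.

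The telephone interviews take place on days 7 and 28 (section 8.5, follow-up after initial assessment). Section 9.2 adds: "Patients will be considered lost to follow-up if telephone interviews were not feasible". It does not separate patients who have died from those who cannot be reached. Section 10.3 treats death as the one serious adverse event that ends participation.

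Section 5.2 makes "Death within 7 days of follow-up" part of clinical failure. Death by day 28 and "Secondary admission to hospital for any reason" are part of the serious adverse outcome.

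Some outcomes can be known without a call. GPs are asked to enter hospitalisation and death within 7 days in the eCRF (9.2) and to complete a short form when a patient returns with deterioration (8.5). Section 7.2 also provides: "An individual patient may also choose to refuse the phone interview, without discontinuing the study itself". The investigators may then use the medical file to day 28.

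The documents give two rules for patients without contact. Section 11.4 states: "Patients who are lost to follow-up will be considered as having had a clinical failure, an adverse outcome". Section 7.2 says of patients who cannot be reached: "They will be excluded from the analysis of the safety of the intervention".

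**The concern.** A per-protocol set is meant to select on adherence. The telephone condition selects on something that happens after enrolment and that one component of the outcome, death, makes impossible. A patient who dies on day 5, with the death entered by the GP, has an observed event and is still removed. A patient who refuses calls but has a complete file to day 28 is removed as well.

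Section 11.2 states a non-inferiority aim for the composite adverse outcome (5% under usual care, margin 2 points) and for activity restriction, and section 11.1 builds no difference in adverse outcomes into the alternative hypothesis. In that setting a per-protocol analysis is the customary check on intention to treat. If events leave the set at a similar rate in each arm, a real excess shrinks and the check leans towards non-inferiority. The two analyses would then also differ for a reason unrelated to adherence.

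**Working it through.** **The plan's own figure.** The documents give no figure for the effect of this exclusion. The nearest is the 80% power for non-inferiority on the composite. With equal true rates of 5%, 210 per arm and no clustering, power = Φ(0.02/√(2 × 0.05 × 0.95/210) − z) = Φ(0.940 − z). That is 15% at one-sided 0.025 and 24% at one-sided 0.05. The 80% is not reproduced on these assumptions; the simulation figure is not shown, so its method cannot be checked. This is a separate matter and does not decide the present point. It does show that the comparison rests on few events.

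**Inputs from section 11.2.** 210 patients per arm, 5% in usual care, margin 2 points. Expected events per arm: 210 × 0.05 = 10.5. Margin in events: 210 × 0.02 = 4.2.

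**Assumptions.** Let f be the share of event patients without complete telephone follow-up. The documents give no value. The 8% in the intervention arm is also assumed. The formula takes f as equal in both arms and all patients without an event as kept.

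**Formula.** Per-protocol rate = p(1 − f)/(1 − fp).

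| f | 5% becomes | 8% becomes | Difference (points) | Events kept of 10.5 and 16.8 |
|---|---|---|---|---|
| 0 | 5.00% | 8.00% | 3.0 | 10.5 and 16.8 |
| 0.1 | 0.045/0.995 = 4.52% | 0.072/0.992 = 7.26% | 2.7 | 9.45 and 15.1 |
| 0.3 | 0.035/0.985 = 3.55% | 0.056/0.976 = 5.74% | 2.2 | 7.35 and 11.8 |
| 0.5 | 0.025/0.975 = 2.56% | 0.040/0.960 = 4.17% | 1.6 | 5.25 and 8.4 |

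The point difference passes below 2 points only when f exceeds about 0.36.

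**Other assumed rates.** For 5% and 7%, the difference of 2.0 points becomes 1.6, 1.1 or 0.4 at f = 0.2, 0.5 or 0.8. For 5% and 9%, 4.0 points becomes 3.3, 2.1 or 0.9.

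**Against a confidence bound.** At f = 0.5 about 204.75 and 201.6 patients remain. The standard error is √(0.0256 × 0.9744/204.75 + 0.0417 × 0.9583/201.6) = 1.79 points. The upper bound is 1.6 + 1.96 × 1.79 = 5.1 points (one-sided 0.025), or 4.5 points at one-sided 0.05, ignoring clustering. With nothing dropped, the standard error is 2.40 points and the 0.025 bound is 3.0 + 1.96 × 2.40 = 7.7 points. The exclusion moves the bound in the favourable direction, but non-inferiority at 2 points would not be shown in either case.

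**What the direction depends on.** If a share g of patients without an event is lost too, f is replaced by 1 − (1 − f)/(1 − g), so only the excess loss among event patients matters. If f differs between arms, the bias can go either way. With true rates of 5% and 7%, f = 0.2 in control and 0.5 in the intervention arm gives 4.04% and 3.63%, a difference of −0.4. The reverse gives 2.56% and 5.68%, a difference of 3.1.

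**The case against.** A reader might infer that the trial's safety comparison, as planned, discards deaths and admissions and would therefore produce a false claim of non-inferiority. The documents do not support that.

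- **No per-protocol safety comparison is specified.** Section 11.2 does not mention the per-protocol set, and the annual safety analysis in 11.4 carries no such restriction. Its use for adverse outcomes is an inference from unrestricted wording and the non-inferiority aim. This stands and makes the point conditional.
- **The main analysis is protected by 11.4**, which counts lost patients as failures and adverse outcomes. This stands as far as 11.4 goes, but 7.2 says the opposite about the safety analysis.
- **Loss of admitted patients is only possible.** The calls are meant to record admissions, and a patient can be reached in hospital or after discharge. Complications do not in themselves prevent a call. Only death necessarily does, and no death rate is given. This stands.
- **Large values of f are unsupported**, and comparing a point estimate with the margin is not a test. Both stand, which is why the table includes 10% and the bound is shown.
- **The calls are protocol procedures** and capture later antibiotic prescriptions, which belong to the primary outcome. Requiring them for a secondary set is therefore arguable for that outcome. It does not justify discarding a documented death from an analysis of adverse outcomes.
- **Other sources are imperfect.** GP entry of events is requested within 7 days, patients may change GP, and GPs know the arm whereas the caller is blinded. This stands and bears on the fix.

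The term complete telephone follow-up is also undefined, so a death reported by a relative might count. That is a reason to define it.

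**Conclusion.** The point holds in conditional form. On its literal wording, 11.4 removes from the per-protocol set every patient who dies before the day-28 call and every call-refuser with a usable file; some patients in hospital on a call day may go too. If the set is used for clinical failure or the serious adverse outcome, which nothing in the plan prevents and the non-inferiority aim makes likely, selection depends on the outcome. The difference is then pulled towards zero, provided loss among event patients is similar across arms and exceeds loss among the others.

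The size cannot be derived from the documents. The fall from 3.0 points to between 2.7 and 1.6 is an illustration that rests on an assumed 8% rate and an assumed loss of 10% to 50% of event patients. The intention-to-treat analysis under 11.4 does not share the defect. The conflict between 7.2 and 11.4 matters more in practice, because following 7.2 would bring a similar contact-based exclusion into the main safety analysis.

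**What to change.** In 11.4:

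1. Define the per-protocol set by adherence to the algorithm plus known status for the outcome being analysed, from any source the trial already collects (telephone, diary, GP eCRF, medical file). Apply the same rule to patients with and without events.
2. Keep every patient with a documented death, admission or complication as an event, whatever telephone contact was made.
3. State which outcomes the per-protocol set serves.
4. Reconcile 7.2 with 11.4 so that one rule governs patients who cannot be reached in the safety analysis.

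The cost is a few sentences and no new data collection. Per-protocol event rates will look less favourable. Some outcomes will come from GPs who know the arm rather than from the blinded caller, so the source of each outcome should be reported by arm.

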4.3 Randomized Intervention Study

Primary Objective

To compare the proportion of antibiotic prescription (at baseline and during the 28-day follow-up) in patients with LRTI managed using UltraPro (intervention arm 1), PCT result only (intervention arm 2) and usual care (routine control arm).

Secondary Objectives

- To compare the clinical outcome of patients with LRTI managed using UltraPro, PCT result only and usual care.
- To evaluate the acceptability and feasibility of the interventions through identification of barriers and facilitators.
- To calculate and compare cost-effectiveness between arms.

Exploratory Objectives

- To describe the aetiologies of LRTIs
- To assess the diagnostic performance of new generation host biomarkers and transcriptomics to predict adverse outcome or to identify patients with pneumonia

5. TO ASSESS THE ASSOCIATION OF SNPs IN GENES INVOLVED IN THE REGULATION OF MICROVASCULAR INTEGRITY WITH ADVERSE OUTCOMESTUDY OUTCOMES

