11.1 Hypothesis

The null hypothesis is that there is no difference in the proportion of antibiotic prescription in patients enrolled in the different arms of the trial.

The alternative hypothesis is that combined use of POCT procalcitonin testing with lung ultrasound leads to significant reduction in antibiotic use with no difference in terms of clinical outcome, duration of the episode, activities restrictions and adverse outcomes.

A reduction of at least 15% in the proportion of patients treated with antibiotics by day 28 is expected as below this threshold, the intervention would be considered as no having a sufficient impact to warrant its implementation at larger scale, at least in its present format.

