11.2 Determination of Sample Size

The sample size was calculated to assess a decrease in antibiotic prescription of at least 15% between the UltraPro and the PCT arms as well as 15% between the PCT arm and usual care.

The proportion of patients receiving antibiotics with the usual care is estimated to be around 60% and to decrease to 45% using PCT and to 30% combining PCT and ultrasound. These numbers have been extrapolated from the subgroup of patients with LRTI in a study at primary care level in the Netherlands [3].

A study sample of 14 GPs and 15 patients per GP in each arm (210 patients per arm and a total of 630 patients) gives a power of 80% to detect a decrease in antibiotic prescription from 60% (usual care) to 45% (PCT), and from 45% (PCT) to 30% (UltraPro), with 5% level of significance, when adjusting for clustering at practice level (intracluster coefficient 0.06) [3]. This sample size guarantees a power of 80% to prove non-inferiority in terms of duration of activities restriction (non-inferiority margin=1 day, standard deviation=4 days) as well as of composite adverse outcome (probability in the “usual care” arm 0.05 with a non-inferiority margin of 0.02). Simulations used to determine the sample size are shown in the following figures.

[figure not shown]

Figure 4: Statistical simulations used to determine sample size

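### The primary comparison of three arms rests on two-group tests with one unsplit 5% level and no order or gate, so the chance of a false primary difference is about 9% to 12%, not 5%

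*Combined protocol and SAP*

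**What the plan says.** Section 4.3 sets one primary objective: to compare antibiotic prescription in patients "managed using UltraPro (intervention arm 1), PCT result only (intervention arm 2) and usual care (routine control arm"). The outcome in section 5.2 is binary: "Proportion of patients prescribed an antibiotic in each arm by day 28".

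Section 11.1 states a single null hypothesis over the arms, that "there is no difference in the proportion of antibiotic prescription in patients enrolled in the different arms of the trial". The alternative in the same section, and the aim in the opening line of section 11, concern the UltraPro strategy only.

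Section 11.2 names two contrasts, a decrease of "at least 15% between the UltraPro and the PCT arms as well as 15% between the PCT arm and usual care". It powers them "from 60% (usual care) to 45% (PCT), and from 45% (PCT) to 30% (UltraPro), with 5% level of significance". The level is given once and is not divided.

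Section 11.4 describes the primary analysis as "Odds ratio of antibiotic prescription between 2 groups as well as the difference in proportion of patients prescribed an antibiotic by day 28". It lists no pairs and gives no significance level of its own. The statistical considerations in the synopsis match it.

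Neither the protocol sections nor the synopsis gives a global test, a testing order, a gate, a multiplicity adjustment or a single named primary contrast. Whether tests are one- or two-sided is not stated.

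**The concern.** The hypothesis is one statement about three arms, but the analysis that is meant to test it is a set of two-group comparisons. Where two or three such tests each use 5%, and any of them may carry the conclusion, 5% is no longer the error rate of that conclusion.

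The gap also leaves a choice open. A claim for the combined strategy could rest on UltraPro v PCT, on UltraPro v usual care, or on whichever is significant. Without a written rule, the headline contrast can be chosen after the results are known.

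**Working it through.** **Inputs.** Three arms, 14 GPs x 15 patients = 210 per arm, ICC 0.06, 5% level, rates 60/45/30 for usual care/PCT/UltraPro (section 11.2), and 1:1:1 allocation of GPs (section 6.2). Two-sided tests are my assumption.

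**The plan's own figure.** The plan states no family-wise error rate. Its stated figure is 80% power for each adjacent contrast.
- Design effect: 1 + (15 − 1) x 0.06 = 1.84. Effective n = 210/1.84 = 114.1 per arm.
- 60% v 45%: pooled SE = √(2 x 0.525 x 0.475/114.1) = 0.0661; unpooled SE = √((0.24 + 0.2475)/114.1) = 0.0654. Power = Φ((0.15 − 1.96 x 0.0661)/0.0654) = Φ(0.31) = 62%.
- 45% v 30%: the same formula gives 65%.

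So 80% does not reproduce with 0.06 read as an ordinary ICC. Read as a random-intercept variance on the logit scale, 0.06 gives ICC = 0.06/(0.06 + π²/3) = 0.018, a design effect of 1.25 and power of 79% and 81%. The documents do not say which is meant, and the simulation figure is not shown. This is a separate question. It sets the base for the power figures below but hardly affects the error rates.

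**Error rate, all arms equal, two-sided 5% tests.**
- *Two powered contrasts.* UltraPro v PCT and PCT v usual care share the PCT arm with opposite signs, so their correlation is −0.5. P(|Z₁| > 1.96 or |Z₂| > 1.96) = 9.1%. Independence would give 1 − 0.95² = 9.75%.
- *All three pairs.* At least one is significant when the studentized range of three means exceeds 1.96 x √2 = 2.77. The probability is 12.2%, or 12.0% with 42 − 3 = 39 degrees of freedom. Independence would give 1 − 0.95³ = 14.3%, and the Bonferroni bound is 15%.
- *False reductions only.* For the two contrasts, 2.5% + 2.5% less a negligible overlap = 5.0%. For three pairs, simulation gives 6.6%. One two-sided test gives 2.5%.
- *If one-sided 5% tests were meant:* 10.0% (two contrasts) or 12.6% (three).

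Simulation of 14 x 15 clustered data at ICC 0.06 with t critical values confirms about 9% and 12%. With a 5% global F test before the pairwise tests it gives 5.0%.

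**Why a gate is enough with three arms.** If all arms are equal, any error must first pass the gate, which happens 5% of the time. If some arms differ, at most one of the three pairwise equalities can be true, because two true ones imply the third. Only one true null is then at risk, and it is tested at 5%. The argument is the same whether the gate is the 2-df arm test or UltraPro v usual care.

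**Power cost (simulation, ICC 0.06, 39 df; rates are usual care/PCT/UltraPro).**

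| Rates | Contrast | No gate | Global gate | UltraPro v usual care first |
|---|---|---|---|---|
| 60/45/30 | each adjacent contrast | 62–63% | 62–63% | 62–63% |
| 60/45/30 | UltraPro v usual care | about 99% | 98.5% | unchanged |
| 60/45/45 | UltraPro v usual care | about 60% | 52–53% | unchanged |
| 60/45/45 | PCT v usual care | about 60% | 52–53% | about 45% |

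At 60/52.5/45, a smaller graded effect, UltraPro v usual care falls by about 13 points under the global gate (63% to 50% on the normal approximation). It is unchanged if tested first.

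**The case against.** **The plan leans towards UltraPro.** The aim and the alternative hypothesis concern the combined strategy, so a lone PCT v usual care result would not establish what the trial set out to show. That is fair. The rule that any significant pair rejects the null is an inference, and no such rule is written. But no formal order is written either, and section 11.2 gives PCT v usual care equal standing in the sample size.

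**The third pair is not listed.** A reader might infer that all three pairs are planned as primary tests. The documents do not say so: section 11.2 names two, and section 11.4 names none. UltraPro v usual care falls within the three-arm objective, so it is possible but not stated. This is why 9% must stand beside 12%.

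**A figure near 15% is tempting.** Wald z tests with 14 clusters per arm give about 14.5% to 15% for three pairs. Part of that is small-sample inflation, since a single z test already errs at about 6.1%. The plan does not specify Wald z tests, and the excess is not multiplicity.

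**The harm is smaller than the headline.** Half or more of the 9% to 12% comes from false increases or mixed directions. This stands, and the false-reduction rates are 5.0% and 6.6%. Section 11.1 also calls reductions under 15% insufficient for implementation. If that were applied to the observed difference, false reductions would drop to about 2% (two contrasts) or 3% (three), but the plan does not make it a test criterion.

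**Control costs power.** Splitting alpha would: at 0.025 per test, 62% and 65% fall to 51% and 54%. A gate avoids this at the planned rates. It would be wrong to call it free in general, as the losses at 60/45/45 and 60/52.5/45 show.

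**Conclusion.** The omission is real and should be repaired. With two-sided 5% tests and no true difference between arms, the chance of at least one false primary difference is about 9% for the two contrasts the plan powers and about 12% if UltraPro v usual care is added. For false reductions alone it is 5.0% and 6.6%, which is two to nearly three times the 2.5% of a single two-sided test.

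These figures assume equal arms of 14 GPs x 15 patients and valid small-sample tests. The choice between 9% and 12% depends on which pairs are primary, and that is what the plan leaves unsaid. The documents do not support 15% as the effect of multiplicity, a settled plan to test all three pairs, or a claim that control is costless.

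**What to change.** In section 11.4, and to match in the synopsis:

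1. Fit one three-arm mixed logistic model with a GP random intercept, using small-sample (t and F) degrees of freedom.
2. State that tests are two-sided.
3. Name the pairwise contrasts, each tested at 5%, and gate them by one of two rules fixed in advance:
   - the 2-df arm test at 5% first, then the three pairs if it is significant; or
   - UltraPro v usual care at 5% first, in line with the stated aim, then the other two pairs if it is significant.

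Either holds the family-wise error at 5% without splitting alpha. The second protects UltraPro v usual care fully. The first is kinder to PCT v usual care if ultrasound adds nothing (52–53% against about 45% at 60/45/45, from about 60% without a gate).

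The cost is one paragraph. Design, sample size and data collection do not change, and the two powered contrasts lose no power at 60/45/30. The choice should be made before outcome data by arm are seen.
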